2. INVESTIGATIONAL PLAN

2.1. Overall Study Design

This is a Phase 1/2a, multi-center, FIH, open-label study consisting of Part A (Phase 1; dose escalation; [Figure 4](#)) followed by Part B (Phase 2a; expansion; [Figure 5](#)).

Part A (Phase 1; dose escalation): At least 24 subjects will receive in “3+3” cohorts escalating doses of CTL-002 IV given as monotherapy or in combination with an anti-PD-1 checkpoint inhibitor in subjects with advanced-stage solid tumors that relapsed post or were refractory to a prior anti-PD-1/PD-L1 therapy.

Note: Enrollment of subjects in Part A (Phase 1; dose escalation phase) of the study has been completed. No further patients will be treated in this part.

Part B (Phase 2a; expansion):

In Part B of the study, various cohorts with defined tumor indications as provided below will be enrolled.

Up to 249 subjects in different expansion cohorts will receive CTL-002 IV in combination with an anti-PD-1 checkpoint inhibitor. In the initial set of expansion cohorts, subjects with advanced-stage, relapsed/refractory solid tumors in non-curable state as per current clinical knowledge and with the following indications will receive treatment with CTL-002 and the defined checkpoint inhibitor:

(1) bladder cancer, hepatocellular cancer, non-small cell lung cancer, cutaneous squamous-cell carcinoma, or melanoma (for melanoma, only cutaneous and mucosal forms, not uveal/ocular) (approved anti-PD-1/PD-L1 indications) that relapsed on or were primary refractory to prior anti-PD-1/PD-L1 therapy with an approved anti-PD-1/PD-L1 compound, or

(2) colorectal cancer (MSS/mismatch-repair competent) and have not received any prior anti-PD-1/PD-L1 therapy, or

(3) biomarker cohort with mixed solid tumors (“basket” cohort) that are relapsed on or were primary refractory to prior anti-PD-1/PD-L1 therapy with an approved anti-PD-1/PD-L1 compound and that have exhausted existing treatment options or are not eligible for them anymore.

- For the **first group**, for bladder cancer, hepatocellular cancer, non-small cell lung cancer and melanoma), N = 14 response-evaluable subjects will be initially recruited per each tumor indication. This shall allow to detect 2 responses in a cohort with 80% probability if the true response rate is 20% or more, and at least 1 response in the cohort with 77% probability if the true response rate is 10% or more. For cutaneous squamous-cell carcinoma, N = 12 response-evaluable subjects will be recruited initially. This should result in 2 responses or more with 80% probability if the true response rate is 25% or higher. For cutaneous squamous-cell carcinoma: Subjects must have locally advanced disease or metastatic disease. Subjects with cutaneous squamous-cell carcinoma with locally advanced disease must not be candidates for surgery for one or both of the following reasons: disease recurrence after two or more surgical procedures and as per treating physician curative resection is unlikely or surgery would result in substantial complications or deformity.

- For the **second group** (colorectal cancer [MSS/mismatch-repair competent], a currently non-approved anti-PD-1/PD-L1 indication), N = 10 response-evaluable subjects will be recruited. This shall allow to detect 1 response with 89% probability (if the true response rate is 20% or more), and 1 response with 80% probability if the true response rate is 15% or more.
- The **third group** (biomarker cohort with mixed solid tumors; “basket” cohort) investigated are subjects with anti-PD-1/PD-L1 relapsed/refractory mixed advanced solid tumors. Initial biomarker analyses by the sponsor for Part A (dose escalation) suggest that Tumor Proportion Score (TPS) PD-L1 might be a biomarker allowing to enrich for responders. In addition, it was shown that 60% of non-melanoma solid tumor patients with PD-L1 TPS ≤ 1 could be transformed from immunologically “cold” tumor status to immunologically “warm/hot”. This cohort is enrolled to further evaluate these preliminary findings and will investigate biomarker and response findings in both groups. In Phase 1, PD-L1 TPS > 1 patient constituted 1/3 of all last-line treated patients. Therefore, up to N = 75 subjects are planned to be enrolled to have at least N = 25 response-evaluable subjects with TPS PD-L1 > 1 status and ideally up to N = 50 response-evaluable subjects with PD-L1 TPS ≤ 1 . For the TPS PD-L1 > 1 group this would ideally confirm a response rate of $\geq 30\%$ (with 81% probability resulting in a minimum of 6 or more responders in the cohort). For subjects with TPS ≤ 1 , a response rate $> 20\%$ would be seen as clinically of interest and beneficial, and this would result in a minimum of 8 (10) responders with a probability of 81% (56%), respectively. If recruitment of 25 response-evaluable subjects with TPS PD-L1 > 1 is achieved, recruitment into the third group will be stopped and the TPS ≤ 1 cohort will be evaluated with given patient number in descriptive way.

For **all groups** the following additional requirements and restrictions apply:

- (a) **All subjects generally must have received a currently for their tumor type approved anti-PD-1/PD-L1 compound**; non-approved, experimental anti-PD-1/PD-L1 treatments are not permissive for enrolment into this group unless condition (e) applies. (Group 2 with MSS-CRC is exempted from this regulation)
- (b) **Baseline tumor biopsies are mandatory for all subjects** to further evaluate for predictive biomarkers of response as detected in Phase 1 and to further deepen the understanding of “cold-to-hot” tumor transitions for response under treatment.
- (c) For **melanoma, cutaneous squamous-cell carcinoma** and the **biomarker cohort with mixed solid tumors** (“basket” cohort), an additional **follow-up, on-treatment biopsy** is mandatory to assess for immunologic changes in the tumor. **Important note:** All biopsies are only taken if considered **safe** and **feasible** by the treating physician/Investigator.
- (d) All subjects that **achieve/maintain stable disease by week 24** but do not show tumor shrinkage beyond – 10% as per RECIST criteria can undergo if desired by the treating physician and agreed by the patient stereotactic radiotherapy of one or more tumor lesions to increase neoantigen exposure and potential for response improvement (as was seen in two Phase 1 patients). This should always be pre-discussed with the medical representative of the sponsor and the radiotherapy area should not include all lesions that are used for RECIST response assessment to allow for abscopal antitumor effect assessment.

Note: In case of initiation of stereotactic radiotherapy in addition to study treatment, an optional tumor biopsy should be performed no earlier than 4 weeks after initiation of radiotherapy, if seen as safe and medically feasible by the treating physician.

For the **third group** (biomarker cohort with mixed solid tumors; “basket” cohort) the following additional requirements and restrictions apply:

- (e) Up to **5 subjects** (but no more) in the PD-L1 TPS > 1 group with **tumor indications that are currently not yet approved at all for anti-PD-1/PD-L1 treatment** may be enrolled if treated with a currently approved anti-PD-1/PD-L1 (for other indication(s)), if also all other criteria for the group apply. For the PD-L1 TPS ≤ 1 group this may be up to 10 patients.
- (f) No subjects with melanoma (cutaneous, mucosal or uveal) can be enrolled into this cohort.

For all cohorts, response is defined as a subject presenting with a partial or complete response to treatment according to RECIST criteria.

If responses are seen and considered to be of interest by number and depth of response, the Safety Review Committee (SRC) may decide in agreement with the Sponsor to expand individual cohorts following a **Simon-2-stage design** to confirm a certain response rate with the following assumptions:

- For the **first group**, for bladder cancer, hepatocellular cancer, non-small cell lung cancer, and melanoma, a minimum of 1 responder each is required to allow for continuation. Treating an additional N = 13 subjects shall generate a total of ≥ 4 responders to assume the overall response rate to be 20% or higher. For cutaneous squamous-cell carcinoma, a minimum of 2 responders is required to allow for continuation. Treating an additional N = 24 subjects shall result in a total of ≥ 6 responders to assume the overall response rate to be 25% or higher
- For the **second group**, for colorectal cancer with N = 10 fixed for the first stage, if at least 1 responder was observed in the first stage, an additional N = 19 subjects may be added to a cohort. In a total of N = 29 subjects at least ≥ 4 responders are expected to assume the true response rate could be at 20% or higher
- For the **third group** (biomarker cohort with mixed solid tumors; “basket” cohort) with up to N = 75 subjects no such further expansion is considered. Instead, depending on response rate, - depth and - duration observed a potential registration size trial design will be considered and reviewed with the competent authorities (separate protocol). For the PD-L1 TPS > 1 group (“hot” tumors) a response rate of ≥ 30% is seen as clinically of significance, for the PD-L1 TPS ≤ 1 (“cold” tumors) a response rate > 20%.

In case of progressive disease (PD), treatment beyond progression might be applied as per Investigator assessment in agreement with the patient.

Proposed indications were selected based upon an **extensive translational research program** by the Sponsor, indicating a negative impact of GDF-15 on the immune response in the tumor microenvironment in the proposed indications, resulting in lack of immune cell infiltration, activation and in some indications proven resistance to checkpoint inhibitor treatment. In all subjects of all cohorts a baseline biopsy is mandatory to evaluate for potential predictive biomarker. In selected cohorts (i.e., melanoma, cutaneous squamous-cell carcinoma and in the

biomarker cohort with mixed solid tumors [“basket” cohort]) sequential, dual tumor biopsies will be taken in subjects with accessible lesions. Enrolment into all cohorts may occur in parallel.

Due to the excellent tolerability of the combination of CTL-002 and nivolumab, the defined checkpoint inhibitor in Part A (Phase 1) of the trial and as per request of Investigators study treatment is made accessible to all subjects with advanced-stage, relapsed/refractory solid tumors in non-curative state as per current clinical knowledge, and the prior, additional requirement to have no therapeutic alternative is removed. For the first and third group in Phase 2a, the requirement of failure or progression on prior anti-PD-1/PD-L1 treatment is maintained.

For the cutaneous squamous-cell carcinoma cohort, combination treatment will be done with cemiplimab (not nivolumab), as the approved checkpoint inhibitor for cutaneous squamous-cell carcinoma treatment.

Subjects interested in participation in the trial are in each case informed about all treatments available for their disease situation. The potential advantages and disadvantages of participating in this experimental trial will be discussed in relationship to available alternative treatment options, among them any remaining approved treatment opportunities. Participating subjects that have still existing alternative treatment options must have understood that these options are available to them, and that trial participation encompasses an experimental treatment. As stated above, subjects enrolling must have completed and failed prior anti-PD-1/PD-L1 in all cases and must be in non-curative state.

Note: Additional cohorts may be added at a later stage to Part B (Phase 2a) of the study but only upon approval of a substantial amendment(s) defining detailed target populations, combination exploration, dose/schedule of CTL-002 for the expansion phase and detailed enrolment criteria of the respective selected target populations. In such an amendment a separate monotherapy cohort may be added to explore the single agent safety profile in detail.

Treatment cycles are as follows:

[figure not shown]
- Q2wk for bladder cancer, hepatocellular cancer, non-small cell lung cancer, melanoma, colorectal cancer and the biomarker cohort with mixed solid tumors (“basket” cohort)
 - 10 mg/kg CTL-002 as an IV infusion over approximately 60 minutes, Q2wk
 - 240 mg nivolumab as an IV infusion over approximately 30 minutes, Q2wk
- Q3wk for the cutaneous squamous-cell carcinoma cohort
 - 20 mg/kg CTL-002 as an IV infusion over approximately 60 minutes, Q3wk
 - 350 mg cemiplimab as an IV infusion over approximately 30 minutes, Q3wk

Pharmaco-modelling and obtained PK/Pharmacodynamic data from Part A (Phase 1) indicate complete GDF-15 neutralization at the dose of 10 mg/kg and the dosing interval of 2 weeks (Q2wk) or the dose of 20 mg/kg and the dosing interval of 3 or 4 weeks (Q3wk or Q4wk), respectively in serum and tumor vasculature (tumor microenvironment) in subjects with a wide range of baseline GDF-15 serum levels. In the current development phase (Phase 2a) the dosing interval follows for subject convenience the dosing interval of the checkpoint inhibitor. No safety events of concern and no DLT have been observed at any dose in Phase 1, including the doses of 10 mg/kg and 20 mg/kg. In addition, the for this initial Phase 2 exploration selected dose of 10 mg/kg and 20 mg/kg (with dosing interval of Q2wk and Q3wk, respectively) provide exposure that is still below the no-observed adverse effect level (NOAEL) in non-human primate (NHP).

Depending on further PK/pharmacodynamics data observed and safety and efficacy data, the SRC may modify these Phase 2 doses if seen as recommended or if a second dose is decided to be explored (all via substantial amendment).

[figure not shown]
Figure 4: Part A (Phase 1; dose escalation)

Note: Enrollment has been completed. No further subjects will be enrolled

Abbreviations: d = day; DL = dose level; DLT = dose-limiting toxicity; PD-1 = programmed death 1; PD-L1 = programmed death ligand 1; q14d = once every 14 days

Figure 5: Part B (Phase 2a; expansion)

Abbreviations: baseBx = baseline biopsy; CA = cancer; CRC = colon adenocarcinoma, rectum adenocarcinoma; CSCC = Cutaneous Squamous-Cell Carcinoma; HCC = Hepatocellular cancer; MSS= microsatellite stability; NSCLC = non-small cell lung cancer; ORR = overall response rate; PD-1 = programmed death 1; PD-L1 = programmed death ligand 1; seqBx = sequential biopsy; TPS = Tumor Proportion Score;

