 - (3) biomarker cohort with mixed solid tumors (“basket” cohort) that are relapsed on or were primary refractory to prior anti-PD-1/PD-L1 therapy with an approved anti-PD-1/PD-L1 compound and that have exhausted existing treatment options or are not eligible for them anymore.
- For the **first group**, for bladder cancer, hepatocellular cancer, non-small cell lung cancer, and melanoma, N = 14 response-evaluable subjects will be initially recruited per each tumor indication. This shall allow to detect 2 responses in a cohort with 80% probability if the true response rate is 20% or more, and at least 1 response in the cohort with 77% probability if the true response rate is 10% or more. For cutaneous squamous-cell carcinoma, N = 12 response-evaluable subjects will be recruited initially. This should result in 2 responses or more with 80% probability if the true response rate is 25% or higher.

For cutaneous squamous-cell carcinoma: Subjects must have locally advanced disease or metastatic disease. Subjects with cutaneous squamous-cell carcinoma with locally advanced disease must not be candidates for surgery for one or both of the following reasons: disease

recurrence after two or more surgical procedures and as per treating physician curative resection is unlikely or surgery would result in substantial complications or deformity.

- For the **second group** (colorectal cancer [MSS/mismatch-repair competent, a currently non-approved anti-PD-1/PD-L1 indication]), N = 10 response-evaluable subjects will be recruited. This shall allow to detect 1 response with 89% probability (if the true response rate is 20% or more), and 1 response with 80% probability if the true response rate is 15% or more.

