Various molecular and immunohistochemical biomarkers and immune parameters (e.g., including but not limited to molecular profiling, mutation status, mutational burden or other markers of interest relating to immune activation or disease may be explored) will be assessed in peripheral blood, serum, urine and tumor tissue.

Statistical Methods:

The sample size for Part A (Phase 1; dose escalation) of the study is not based on any statistical assumptions; rather, it follows the classic '3+3 rule', a well-established methodology in the design of dose-finding clinical trials in oncology.

The study plans for up to 5 dose escalation cohorts in Part A, with each cohort comprising a minimum of 3 subjects to be treated with CTL-002 in combination with the defined checkpoint inhibitor at each dose escalating level and with typical DLT driven expansions up to 6 subjects per cohort and at the MTD.

In Part B (Phase 2a; expansion), cohorts with several defined tumor indications will be treated to detect efficacy signals, in a screening effort to identify tumor indications where CTL-002 has clinically relevant antitumor activity. All indications have been selected based upon translational research results by the

sponsor and other scientific groups that indicate an immunosuppressive role of GDF-15 in these tumor indications.

To achieve this and based upon a **conditional probability calculation** the following subject numbers are recruited:

- For the **first group**, for bladder cancer, hepatocellular cancer, non-small cell lung cancer, and melanoma, N=14 response-evaluable subjects will be initially recruited per each tumor indication. This shall allow to detect 2 responses in a cohort with 80% probability if the true response rate is 20% or more, and at least 1 response in the cohort with 77% probability if the true response rate is 10% or more. For cutaneous squamous-cell carcinoma, N = 12 response-evaluable subjects will be recruited initially. This should result in 2 responses or more with 80% probability if the true response rate is 25% or higher.
- For the **second group** (colorectal cancer [MSS/mismatch-repair competent, a currently non-approved anti-PD-1/PD-L1 indication]), N=10 response-evaluable subject will be recruited. This shall allow to detect 1 response with 89% probability (if the true response rate is 20% or more), and 1 response with 80% probability if the true response rate is 15% or more.

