- For the **third group** (biomarker cohort with mixed solid tumors; “basket” cohort), N = 75 subjects are planned to be enrolled to have at least N = 25 response-evaluable subjects with TPS PD-L1 > 1 status and ideally up to N = 50 response-evaluable subjects with PD-L1 TPS ≤ 1. For the TPS PD-L1 > 1 group this would ideally confirm a response rate of ≥ 30% (with 81% probability resulting in a minimum of 6 or more responders in the cohort), resulting in a lower limit of the 95% confidence interval of 0.15 (15% lower end response rate), allowing to well rule out background response rates at 5-10% level. For subjects with TPS ≤ 1, a response rate > 20% would be seen as clinically of interest and beneficial, and

this would result in a minimum of 8 (10) responders with a probability of 81% (56%), respectively, if the true response rate is 20% or above. If recruitment of 25 response-evaluable subjects with TPS PD-L1 > 1 is achieved, recruitment into the third group will be stopped and the TPS ≤1 cohort will be evaluated with given patient number in descriptive way.

Response is defined as a subject presenting with a partial or complete response to treatment according to RECIST criteria.

If responses are seen and considered to be of interest by number and depth of response, the SRC may decide in agreement with the Sponsor to expand individual cohorts **following a Simon-2-stage design** to confirm a certain response rate with the following assumptions:

- For the **first group**, for bladder cancer, hepatocellular cancer, non-small cell lung cancer, and melanoma with N = 14 fixed for the first stage, an additional N = 13 subjects may be added to a cohort to achieve at least 4/27 responders and confirms a true response rate of 20% with 80% power. For cutaneous squamous-cell carcinoma, N = 12 fixed for the first stage, an additional N = 24 subjects may be added to a cohort to achieve at least 6/36 responders and confirm a true response rate of 25% with 80% power.
- For the **second group**, for colorectal cancer with N = 10 fixed for the first stage, an additional N = 19 subjects may be added to a cohort to achieve at least 4/29 responders and confirm the true response rate of 20% with 80% power.

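### CSCC stage 1: the stated 80% probability of 2 or more responses in 12 subjects at a 25% response rate should read 84%

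*Protocol*

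**What the plan says.** Section 2.1 sets the stage-1 size: "For cutaneous squamous-cell carcinoma, N = 12 response-evaluable subjects will be recruited initially". The justification follows directly: this size should give "2 responses or more with 80% probability", provided the true response rate is at least 25%. The same pair of statements is in the Synopsis under Overall Study Design (Part B), in the Synopsis under Statistical Methods, and in Section 8.1.

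Two related statements use the same cohort and the same 25% rate. Section 2.1 gives the stage-1 minimum: "For cutaneous squamous-cell carcinoma, a minimum of 2 responders is required to allow for continuation". Section 8.1, like the Synopsis under Statistical Methods, gives the two-stage target after 24 more subjects: "at least 6/36 responders and confirm a true response rate of 25% with 80% power".

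Section 8.1 presents the Part B cohort sizes as resting on a probability calculation, so the 80% is the stated operating characteristic behind N = 12.

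**The concern.** Every input needed to check the 80% stands beside it: 12 subjects, at least 2 responses, a true rate of 25%. The binomial probability from those inputs is not 80%. The neighbouring probabilities, worded in much the same way, do check out. A reader verifying the design would therefore conclude that either the N or the probability for CSCC is wrong, and the text does not say which.

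The stake is the accuracy of a stated operating characteristic. Two responders is also the CSCC minimum for continuation, so the figure tells the reader how likely a cohort with a 25% rate is to meet that minimum.

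**Working it through.** **Inputs** (Section 2.1): n = 12 response-evaluable subjects; threshold of 2 or more responses; true response rate p = 0.25, the boundary of the stated range.

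**Formula.** With X ~ Binomial(n, p), P(X ≥ 2) = 1 − (1 − p)^n − n·p·(1 − p)^(n − 1).

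**CSCC figure.**
- 0.75^12 = 0.0317
- 12 × 0.25 × 0.75^11 = 0.1267
- P(X ≥ 2) = 1 − 0.0317 − 0.1267 = 0.842, against the stated 0.80: a difference of 4.2 points.

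**Does the protocol use the exact binomial elsewhere?** The same calculation for the other stage-1 and basket statements (Sections 2.1 and 8.1):

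| Cohort | n | Responses | True rate | Stated | Exact binomial |
|---|---|---|---|---|---|
| Bladder, HCC, NSCLC, melanoma | 14 | ≥ 2 | 20% | 80% | 80.2% |
| Same | 14 | ≥ 1 | 10% | 77% | 77.1% |
| Colorectal | 10 | ≥ 1 | 20% | 89% | 89.3% |
| Same | 10 | ≥ 1 | 15% | 80% | 80.3% |
| Basket, TPS > 1 | 25 | ≥ 6 | 30% | 81% | 80.7% |
| Basket, TPS ≤ 1 | 50 | ≥ 8 | 20% | 81% | 81.0% |
| Same | 50 | ≥ 10 | 20% | 56% | 55.6% |
| **CSCC** | **12** | **≥ 2** | **25%** | **80%** | **84.2%** |

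Seven of eight agree to the nearest point. Only CSCC does not.

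**Could another method give 80%?** For n = 12 and p = 0.25, the normal approximation gives 84.1% with continuity correction and 74.8% without. A Poisson approximation with mean 12 × 0.25 = 3 gives 1 − e^(−3)·(1 + 3) = 80.1%. It would have had to be used for this cohort alone, and nothing in the protocol suggests that.

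**Two-stage power, as a cross-check.** The rule is to continue with at least 2 of 12 and succeed with at least 6 of 36. At p = 0.25 the power is the sum over x = 2 to 12 of P(X₁ = x)·P(X₂ ≥ max(0, 6 − x)), with X₁ ~ Binomial(12, 0.25) and X₂ ~ Binomial(24, 0.25). This gives 80.3%, which agrees with the stated 80%. The two-stage figure is correct; only the stage-1 figure is off.

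**The case against.** The strongest defence is that the sentence is conditional: "if the true response rate is 25% or higher". Over that whole range the probability is at least 84.2%, so 80% holds everywhere as a loose floor. The error also runs in the safe direction, and the study is described as exploratory. The conservative direction stands and keeps the point small. The floor reading does not remove it. The sister statement for N = 14 has the same construction, "This shall allow to detect 2 responses in a cohort with 80% probability if the true response rate is 20% or more", and its figure is the exact value at the boundary rate. By the protocol's own convention the CSCC figure is a point value at 25%, and the text does not say at least 80%.

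Three stronger readings are tempting, and the protocol does not support them.

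- **That the 80% was calculated for N = 11.** Eleven subjects would give 80.3%, but N = 11 appears nowhere. The two-stage power for 12 and 36 subjects is also 80.3%, so the number could equally have been carried over from there. Its origin cannot be established.
- **That the protocol states a 20% risk of wrongly stopping CSCC.** No such risk is written. It is only the complement of the 80%.
- **That 84.2% is the probability of expansion, so that the stopping risk is 16%.** Two responders is necessary but not sufficient. Under Sections 2.1 and 7.4 expansion also requires that the number and depth of responses are judged of interest, that safety warrants it, and that the SRC and the Sponsor agree. The 84.2% is therefore an upper bound on the chance of expansion at a 25% rate.

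**Conclusion.** The stated probability is wrong as written: 80% should be 84% (exact value 84.2%). The result assumes only independent responses with a common true rate of exactly 25% among 12 response-evaluable subjects, the same basis on which the protocol's other figures reproduce.

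The figure describes the chance of reaching the minimum of 2 responders and nothing more. The error understates the design's performance. It leaves N = 12, the 2-responder minimum, the 6-of-36 rule and the two-stage power untouched. This is a minor correction.

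The figure to change is the probability, not the N. Twelve is given consistently as the CSCC stage-1 size in Sections 2.1, 2.2.2 and 8.1, and the 36-subject design is 12 + 24. The stage-1 total of 79 in Section 8.5 should not be cited as further support, because the stated cohort sizes add to 4 × 14 + 12 + 10 = 78.

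**What to change.** Replace 80% with 84% in the CSCC stage-1 sentence in all four places: Synopsis, Overall Study Design (Part B); Synopsis, Statistical Methods; Section 2.1; Section 8.1. Keep N = 12 and the minimum of 2 responders. Leave the 80% two-stage power in the Synopsis (Statistical Methods) and Section 8.1 unchanged. Do not add a stopping-risk figure, because expansion depends on more than the responder count.

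The cost is one number edited in four places, with no effect on sample size, decision rules or conduct.

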8.5. Sample Size

The sample size for Part A (Phase 1; dose escalation) of the study is not based on any statistical assumptions; rather, it follows the classic ‘3+3 rule,’ a well-established methodology in the design of dose-finding clinical trials in oncology.

The study plans for up to 5 dose escalation cohorts in Part A, with each cohort comprising a minimum of 3 subjects to be treated with CTL-002 in combination with the defined checkpoint inhibitor at each dose escalating level and with typical DLT driven expansions up to 6 subjects per cohort and at the MTD.

For Part A of the study (Phase 1; dose escalation), it is anticipated that a minimum of 24 subjects will be enrolled.

For Part B of the study (Phase 2a; expansion), up to 249 subjects will be enrolled in different expansion cohorts (79 response evaluable subjects in the first cohorts, with expansion option of 4×13, 1×24 and 1×19 subjects = 95 subjects, and 75 subjects in the biomarker cohort with mixed solid tumors; “basket” cohort). Therefore, a total of approximately 274 subjects might be enrolled (Part A: n = 25 / Part B: n = 79 + 95 + 75 = 249). Additional cohorts may be added via substantial amendment, only.

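### The basket's 75 subjects give 25 PD-L1 TPS > 1 subjects only on average, its quoted response probabilities assume fixed subgroup sizes, and the Part B total is one too high

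*Protocol*

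**What the plan says.** Protocol section 2.1 (third group), repeated in the synopsis, gives the basis for the basket size: "In Phase 1, PD-L1 TPS > 1 patient constituted 1/3 of all last-line treated patients". From this it concludes that "up to N = 75 subjects are planned to be enrolled to have at least N = 25 response-evaluable subjects with TPS PD-L1" > 1, and "ideally up to N = 50 response-evaluable subjects with PD-L1 TPS" ≤ 1. The same paragraph gives the probabilities attached to those sizes. For TPS > 1 at a 30% response rate the design is described as "with 81% probability resulting in a minimum of 6 or more responders in the cohort". For TPS ≤ 1 at 20% it is "a minimum of 8 (10) responders with a probability of 81% (56%), respectively".

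Section 8.1 adds the recruitment rule: "If recruitment of 25 response-evaluable subjects with TPS PD-L1 > 1 is achieved, recruitment into the third group will be stopped". The TPS ≤ 1 group is then described at whatever size it has reached.

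For the tumor-specific cohorts of bladder cancer, hepatocellular cancer, lung cancer and melanoma, section 2.1 states that "N = 14 response-evaluable subjects will be initially recruited per each tumor indication". It sets 12 for cutaneous squamous-cell carcinoma and 10 for colorectal cancer. Section 8.5 totals these as "79 response evaluable subjects in the first cohorts, with expansion option of 4×13, 1×24 and 1×19 subjects = 95 subjects", adds the basket's 75 to reach 249, and adds 25 from Part A to reach 274. It describes the 249 as the maximum to be enrolled. Sections 2.2.2 and 3.5 provide for replacing subjects who are not response-evaluable.

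**The concern.** A cap of 75 is presented as securing a minimum of 25 TPS > 1 subjects, yet it is the number that yields 25 on average. A size set at the mean misses its target about half the time, before any loss. The response probabilities are quoted as if both subgroup sizes were certain, whereas the stopping rule makes them random and ties one to the other.

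The basket has no second stage. Its response rates are to inform whether a registration-size trial is considered, so a reader should see how often the cohort delivers the information described. The Part B total is a plain sum of fixed integers and ought to match its parts. A maximum for enrolment should also make clear whether the replacements the protocol foresees fall inside it.

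**Working it through.** **Inputs.** Cap 75, share 1/3, targets 25 and 50, response rates 30% and 20% (sections 2.1 and 8.1). Stop at the 25th evaluable TPS > 1 subject (8.1). Cohort sizes 14 (four cohorts), 12 and 10 (2.1). Expansion sizes 4 × 13, 24 and 19 (8.5). The protocol gives no non-evaluable rate, so 5% and 10% below are assumptions.

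**1. The plan's own figures.** 25 / (1/3) = 75 and 75 × 2/3 = 50, which requires every subject to be evaluable. Binomial tails at fixed size:
- P(≥ 6 of 25 at 0.30) = 80.7%; stated 81%.
- P(≥ 8 of 50 at 0.20) = 81.0%; stated 81%.
- P(≥ 10 of 50 at 0.20) = 55.6%; stated 56%.

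All three reproduce.

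**2. Chance of reaching 25.** With X ~ Binomial(75, p × e), where p is the TPS > 1 share and e the evaluable fraction:
- p = 1/3, e = 1: P(X ≥ 25) = 54.3%.
- p = 1/3, e = 0.95: 42.0%; e = 0.90: 30.3%. These apply only if lost subjects are not replaced outside the 75.
- e = 1, p = 0.25: 6.6%; p = 0.40: 90.4%.

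**3. Response probabilities under the cap and the stopping rule.** With all subjects evaluable there are two kinds of outcome:
- Recruitment stops at subject n (25 to 75) with probability C(n−1, 24) p^25 (1−p)^(n−25), leaving 25 TPS > 1 and n − 25 TPS ≤ 1 subjects.
- The cap is reached with x < 25 TPS > 1 subjects, with probability C(75, x) p^x (1−p)^(75−x), leaving 75 − x TPS ≤ 1 subjects.

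Averaging the binomial response tails over these outcomes gives:

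| TPS > 1 share | ≥ 6 responders, TPS > 1, 30% | ≥ 8 responders, TPS ≤ 1, 20% | ≥ 10 responders, TPS ≤ 1, 20% |
|---|---|---|---|
| Stated | 81% | 81% | 56% |
| 1/3 | 73% | 71% | 47% |
| 25% | 49% | 89% | 70% |
| 40% | 80% | 46% | 24% |

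At 1/3, if an assumed 10% are non-evaluable and not replaced outside the 75, the row becomes 66%, 65% and 38%. The mean TPS ≤ 1 count at 1/3 with no losses is 46.8. The matching TPS > 1 mean is 46.8 × (1/3)/(2/3) = 23.4, below 25 because the stop removes every count above 25 while the cap leaves the shortfalls.

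**4. Totals.** Stage 1: 4 × 14 + 12 + 10 = 56 + 12 + 10 = 78, not 79. Expansion: 52 + 24 + 19 = 95, as stated. Part B: 78 + 95 + 75 = 248, not 249. Study: 25 + 248 = 273, not 274.

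**The case against.** The printed probabilities are not miscalculated. They are correct given 25 and 50 subjects, section 8.1 calls their basis a conditional probability calculation, and quoting detection chances at the target size is usual. The study is declared explorative, and no test or go/no-go boundary in the basket hangs on them. This stands: the defect is that the condition on subgroup size is not stated, and that the protocol's own rule makes the condition uncertain.

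The loss scenarios are also open to challenge. No non-evaluable rate is given, section 3.5 counts subjects with confirmed progression or a toxicity discontinuation as evaluable, and replacement is foreseen. If replacements fall outside the 75, only the no-loss figures apply. The 1/3 itself comes from a Phase 1 part of 25 subjects, so 54% should not be read as precise.

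Two stronger readings are tempting and are not supported. A reader might infer a broken promise from the fact that 25 and 50 are reached together only when the 25th TPS > 1 subject is exactly the 75th enrolled: C(74, 24)(1/3)^25(2/3)^50 = 3.2%. But 50 is worded as an ideal upper size, and a smaller, descriptively evaluated group is expressly foreseen. A reader might also divide all 248 by 0.9 and conclude that 276 must be enrolled. That treats the basket's 75 as evaluable subjects when the text makes it an enrolment figure, and the 95 expansion subjects are not called response-evaluable in section 8.5 either.

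Finally, the sum error is one subject, in a total the protocol calls approximate.

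**Conclusion.** The point holds in a limited form. The firm shortfall is the minimum of 25: at the protocol's own share and with no losses, a cap of 75 meets it 54% of the time, with a range of about 7% to 90% for shares of 25% to 40%. The three response probabilities are right only conditional on subgroup sizes of 25 and 50. Under the stated cap and stop they fall by roughly 8 to 10 percentage points, to about 73%, 71% and 47%, at a share of 1/3 with all subjects evaluable. The figures with losses depend on an assumed rate and on replacements being counted inside the 75.

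The stage-1 subtotal and both totals are each one too high. This is a small slip but a certain one. The stage-1 count is labelled response-evaluable yet placed inside an enrolment maximum, with no statement of where replacements are counted. None of this undermines the design; it means the sample-size text claims more than its own rule delivers.

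**What to change.** In the synopsis and sections 2.1, 2.2.2, 8.1 and 8.5, wherever the figures appear:
- Replace the minimum of 25 with wording such as: about 25 TPS > 1 subjects expected among 75 enrolled (about a 54% chance of at least 25 at a share of 1/3 if all are evaluable).
- Label 81%, 81% and 56% as conditional on 25 and 50 evaluable subjects. Add 73%, 71% and 47% as the values under the cap and stopping rule, with the 1/3 share and full evaluability stated as assumptions.
- Correct 79, 249 and 274 to 78, 248 and 273.
- Label only the stage-1 78 as response-evaluable, keep 75 as an enrolment cap, and state whether replacements count within 75 and within 248.

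The cost is a text correction. The stated probabilities become less favourable; the design need not change, and no subjects are added beyond replacements already foreseen.
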